#### **4.6 Subject replacement**

Subjects withdrawn prematurely in Part 1 will be replaced in order to achieve 6 subjects that complete all Visit 2-assessments.

## 5 TREATMENTS

A separate instruction will cover all procedures regarding handling, dilution, and administration of the IMPs. The manual will be provided to the clinical investigational unit before the start of the study.

### 5.1 Treatments Administered

#### 5.1.1 Investigational Medicinal Product

The IMPs in this trial are FE 204205 10 mg/mL and placebo (commercially available 0.9% sodium chloride).

##### 5.1.1.1 Part 1

In Part 1, each subject will receive three ascending doses of FE 204205, given once daily as 2-hour intravenous infusions on three consecutive days.

**Table 5-1 Planned dose regimen of FE 204205, Part 1**

(Doses to be infused i.v. over 2 hours and respective infusion rates)

Treatment Day	Dose (Patients 1-3)	Dose (Patients 4-6)
Day 1	0.01 mg (0.005 mg/hr)	0.025 mg (0.0125 mg/hr)
Day 2	0.025 mg (0.0125 mg/hr)	0.05 mg (0.025 mg/hr)
Day 3	0.05 mg (0.025 mg/hr)	0.1 mg (0.05 mg/hr)

Planned doses and infusion rates are listed in Table 5-1. After the first 3 patients have completed all Visit 2 assessments, the SRC will evaluate the preliminary safety, tolerability, and pharmacodynamics data of the FE 204205 and will decide if the dosing regimen can be increased as planned, or if a modified (lower) dose regimen should be applied. A modified dosing regimen may be chosen by the SRC (also in unscheduled meetings, if deemed necessary by the Investigator or Sponsor) as long as the modified planned infusion rates do not exceed the infusion rates given in Table 5-1, and as long as the modified increments between the dosing days (from Day 1 to Day 2 and from Day 2 to Day 3) do not exceed factor 2.

##### 5.1.1.2 Part 2

In Part 2, each subject will receive a single 2-hour intravenous infusion of FE 204205 or placebo.

The SRC will evaluate the safety and tolerability of the compound after the completion of Part 1 to determine the maximum tolerated dose within the administered dose range of FE 204205, and recommend which dose to be investigated in Part 2.

### 5.1.2 Non-Investigational Medicinal Product

Commercially available 0.9% sodium chloride to be used for dilution of IMP will be supplied by the Sponsor. Commercially available midazolam for sedation, mepivacaine for local anaesthesia, and the contrast medium iodine will be provided by the site.

### 5.2 Characteristics and Source of Supply

The IMPs are provided by Ferring Pharmaceuticals A/S and will be handled according to the principles of Good Manufacturing Practice (GMP). Ferring Pharmaceuticals A/S will provide the pharmacy at University of Barcelona, Hospital Clinic with IMP and non-IMP in amounts sufficient for the trial.

#### 5.2.1 Investigational Medicinal Products

The stock solution of FE 204205 is detailed in (Table 5-2). FE 204205 will be diluted with 0.9% sodium chloride to the desired concentrations. Commercially available 0.9% sodium chloride will be used as placebo.

**Table 5-2 Composition of IMP**

	FE 204205
FE 204205	10 mg/mL
Sodiumacetate buffer	10 mM, pH4.5
Mannitol	44.3 mg/mL
Sodiumchloride	---

### 5.3 Packaging and Labelling

Packaging and labelling of the medicinal products will be performed under the responsibility of the IMP department at Ferring Pharmaceuticals A/S in accordance with GMP and national regulatory requirements.

The IMP will be labelled according to Annex 13, EudraLex Volume 4 and national regulatory requirements. The label of the IMP will contain one self-adhesive tear-off portion to be affixed to the Subject dispensing log, or similar, maintained at the trial site. The IMPs will be labelled with a unique IMP number.

### 5.4 Conditions for Storage and Use

Storage condition is stated at the labels of the IMP and non-investigational medicinal product (non-IMP). The Investigator will ensure that the IMPs and non-IMP will be stored according to storage condition at the label, in a secure location with controlled access. The storage compartments shall be monitored regularly and the temperature shall be documented. Deviations in storage temperature must be reported to Sponsor without delay and the IMP must not be used until acceptance from the Sponsor is received.

## 5.5 Blinding / Unblinding

### 5.5.1 Blinding

Part 1 of the trial is open-labelled. In Part 2, all subjects, the Investigator, and all staff involved in the conduct of the trial will be blinded to the treatment received. The trial monitor will not be blinded, and no specific precautions will be taken to keep the pharmacist or personnel running the analyses of FE 204205 blinded.

It is the responsibility of the pharmacy to ensure that the syringes used for infusion in Part 2 are identical and non-distinguishable.

The pharmacy will receive the computer-generated randomisation list from Global Biometrics, Ferring Pharmaceuticals A/S.

### 5.5.2 Unblinding of Individual Subject Treatment

An emergency decoding system will be available to the Investigator at University of Barcelona Hospital Clinic and to designated persons at Ferring Pharmaceuticals for each subject. Breaking of the blind for individual subjects in emergency situations is only permitted in case of a serious, unexpected, or other important AE, when the knowledge of the trial medication in question is required for therapeutic decisions and for the management of the subject. As far as the emergency permits, the need to break the blind will be agreed by the Investigator and Ferring. If the blinding is broken it must be documented by whom, reason and the date of unblinding.

If it is necessary to unblind an individual subject's treatment for the purposes of expedited reporting to the authorities and/or IEC, only those individuals within Ferring whose responsibility it is to report this information will know the identity of the trial medication. Every attempt will be made to try to keep all other trial and site personnel blinded throughout the course of the trial.

Information on whether the blind has been broken for any subjects must be collected before the database is declared clean and is released to the statistician.

If unblinding is deemed appropriate, the blinding for a patient need not be kept once the patient have been treated and all data are entered in the eCRF.

## 5.6 Treatment Compliance

### 5.6.1 Dispensing and Accountability

The Investigator will maintain a drug accountability logs or equivalent detailing the dates and quantities of study medication dispensed to, and used by, each subject, as well as the batch numbers. The Monitor will verify the drug accountability during the trial.

### 5.6.2 Assessment of Compliance

The study medication will be administered by authorised staff at the clinical investigation unit. Compliance is assessed by recording the volume infused.

## **5.7 Auxiliary Supplies**

University of Barcelona, Hospital Clinic, will use auxiliary supplies as instructed by Ferring Pharmaceuticals A/S. The materials will be provided from commercial lots and supplied by the site. No modification to the commercial state will be made.

## **5.8 Return and Destruction of Medicinal Products and Auxiliary Supplies**

Used IMP vials, sodium chloride infusion bags, and auxiliary supplies used for dilution and infusion will be destroyed at site according to local regulations and standard procedures at the site after the drug accountability has been verified by the Monitor and signed off by the Sponsor.

Documentation on destruction will be forwarded to the Sponsor.

Any unused IMP and sodium chloride will be returned for destruction, as instructed by IMP Department, Ferring Pharmaceuticals A/S, and in accordance with local requirements, after the drug accountability has been finalised, verified by the Monitor, signed off by the Investigator, and approved by the Sponsor.

## 6 TRIAL PROCEDURES

For each subject, the duration of the treatment period, including the screening period and the follow-up visit will not exceed 5 weeks. Assessments of concomitant medication and AEs will be performed throughout both study periods.

FE 204205 or placebo will be administered as a continuous 2-hour intravenous infusion starting in the morning. The infusion may be paused or slowed down if tolerability issues arise. The patient will be monitored during the infusion, including assessment of pulse rate and blood pressure.

### 6.1 Part 1

Each patient will receive three ascending doses of FE 204205, given once daily as 2-hour infusions on three consecutive days.

#### Visit 1 (Screening, Day -21 to Day -1)

At the screening visit each subject will be informed about the study and after signing the Informed Consent form assessments for eligibility will commence. The eligibility evaluation includes adherence to inclusion and exclusion criteria, collection of concomitant medication, demographic data and medical history, physical examination, urine drug screen, alcohol urine test, assessment of vital signs and 12-lead ECG, blood sampling for serology, pregnancy test, and clinical chemistry, haematology, and urine sampling for urinalysis (i.e. clinical laboratory parameters).

#### Visit 2 (Residential stay, Day -1 to Day 4)

Subjects found eligible will be asked to return for a treatment visit (residential stay). At the arrival to the clinic on the day before the first administration day (Day -1), a general eligibility check (inclusion/exclusion criteria, medical history, urine drug screen, alcohol urine test, assessment of vital signs and 12-lead ECG, pregnancy test, blood and urine sampling for clinical laboratory parameters) will be performed. A baseline assessment of venous blood gases including lactate will also be performed.

The next day (Day 1) subjects will be dosed with a 2-hour continuous intravenous infusion of FE 204205 (for planned doses see Protocol Section [5.1.1.1](#)). Before administration of FE 204205 the subjects body weight will be assessed. Safety assessments including sampling for clinical laboratory parameters, assessment of vital signs, 12-lead ECG, venous blood gases including lactate, and urinary output will be performed at predetermined time-points ([Table 6-1](#)). Blood samples for pharmacokinetic determination, metabolites, biomarkers, and samples for urinary biomarkers and excretion of FE 204205 and metabolites will be collected at predetermined time-points ([Table 6-1](#)).

On Day 2 and Day 3 the subject will be administered ascending doses of FE 204205 through 2-hour continuous infusions. Before each administration of FE 204205 the subjects body weight will be assessed. Safety assessments including sampling for clinical laboratory parameters, assessment of vital signs, 12-lead ECG, venous blood gases including lactate, and urinary output will be

performed at predetermined time-points ([Table 6-1](#)). Blood samples for pharmacokinetic determination, metabolites, biomarkers, and samples for urinary biomarkers and excretion of FE 204205 and metabolites will be collected at predetermined time-points ([Table 6-1](#)). On Day 3, in addition to the same assessments performed on Day 2, systemic and portal haemodynamics will be assessed by pulmonary artery and hepatic vein catheterization with measurements performed at pre-determined time-points before, during and immediately after the intravenous infusion ([Table 6-1](#)).

HVPG is the golden standard for evaluation of portal hypertension in patients with cirrhosis. It is a moderately invasive technique and catheterization of the patients will be carried out under mild sedation with midazolam and local anaesthesia. A balloon-tipped catheter is placed in the right or middle hepatic vein and the FHVP and WHVP are measured, the latter is when the vein is occluded by the balloon.

After an overnight fast, the patients will be transferred to the Hepatic Haemodynamic Laboratory. Under mild sedation and local anaesthesia, a venous catheter introducer will be placed using ultrasonographic guidance in the right jugular vein by the Seldinger technique. Under fluoroscopic control, a Swan-Ganz catheter will be advanced to the pulmonary artery for measurement of baseline (pre-dose) cardiopulmonary pressures and cardiac output by the thermal dilution method. After withdrawal of the Swan-Ganz catheter, a balloon-tipped catheter will be guided using fluoroscopy into the inferior vena cava and subsequently to the main right or middle hepatic vein for measurements of baseline (predose) FHVP, WHVP, and IVC. The HVPG results from the difference between WHVP (occluded) and FHVP. The adequacy of occlusion will be checked by gentle injection of a small amount of radiologic contrast medium after balloon inflation. All measurements will be performed at least in duplicate (the average will be used for the endpoint) and permanent tracings will be obtained with a multichannel recorder and adequately calibrated transducers. The catheter will be kept in the hepatic vein for assessments of FHVP and WHVP at 1 and 2 hours after start of infusion of IMP. At withdrawal of the catheter (at 2 hours after start of infusion) IVC will be reexamined. Immediately after the removal of the balloon-tipped catheter, cardiopulmonary pressures and cardiac output will be reassessed (at 2 hours after start of infusion) using a Swan-Ganz catheter advanced to the pulmonary artery under fluoroscopic control. During the haemodynamic study all patients will be subjected to noninvasive monitoring by continuous display of heart rate, pulse oximetry, and respiratory rate, along with frequent blood pressure measurements.

The subjects will be discharged from the clinic after the post-dose assessments (clinical laboratory parameters, vital signs, 12-lead ECG, body weight) on Day 4 ([Table 6-1](#)) have been performed.

### Visit 3 (Follow-up, Day 7 to Day 14)

A follow-up visit will be performed 4-11 days after the last administration, and will be considered end of study. At this visit a physical examination, assessment of vital signs and 12-lead ECG

recording will be performed, pregnancy test, and samples for clinical laboratory parameters will be collected.

**Table 6-1 Study Flow Chart, Part 1**

Assessment	Screening	Treatment Period					End of trial
Visit No.	Visit 1	Visit 2					Visit 3
Procedures / Days	-21 to -1	Day -1	Day 1	Day 2	Day 3	Day 4	Days 7-14
Informed consent	X						
Inclusion and exclusion criteria	X	X					
Demographics	X						
Physical examination	X						X
Medical history	X	X					
Clinical chemistry, haematology, urinalysis	X	X	X 	X 	X 	X 	X
Serology/virology	X						
Urine drug screen	X	X					
Alcohol urine test	X	X					
Pregnancy test (serum)	X	X					X
12-lead ECG	X	X	X 	X 	X 	X 	X
Vital signs (non-invasive)	X	X	X 	X 	X 	X 	X
Adverse events	X	X	X	X	X	X	X
Concomitant medication	X	X	X	X	X	X	X
Venous blood gas including lactate		X	X 	X 	X 		
Administration of FE 204205			X	X	X		
Blood samples for PK and metabolites				X 	X 	X 	
Hepatic vein and pulmonary artery catheterization						X 	
Blood biomarkers				X 	X 	X 	
Urine sampling for urinary output, urinary biomarkers and excretion of FE 204205 and metabolites				X 	X 	X 	
Body weight				X 	X 	X 	X 

 Blood samples for safety laboratory evaluations will be collected 6 hours after start of infusion on Days 1-3, and in the morning on Day 4.

 ECG will be collected pre-dose and at 1, 2, 3, and 6 hours after the start of the infusion on Days 1-3, and in the morning on Day 4.

 Vital signs comprising systolic and diastolic arterial blood pressure (including calculation of mean arterial pressure) and pulse will be assessed pre-dose, every 5 min until 30 min after start of infusion, then every 10 min until 1 hour after start of infusion, then every 15 min until 2.5 hours after start of infusion and thereafter 3, 4, and 6 hours after start of infusion on Days 1-3, and in the morning on Day 4. Temperature only pre-dose and 6 hours after start of infusion on Days 1-3.

 Venous blood gas including lactate will be collected 3 hours after the start of the infusion on Days 1-3.

 Blood samples for measurement of plasma concentration of FE 204205 and metabolites will be collected pre-dose and at 0.5, 1, 2, 3 and 4 hours after the start of the infusion on Days 1-3.

 Blood samples for measurement of biomarkers will be collected pre-dose and at 3 hours after the start of the infusion on Days 1-3.

 Urinary output, urinary biomarkers and excretion of FE 204205 and metabolites will be measured pre-dose and after each spontaneous void up to 8 hours after start of infusion on Days 1-3.

 Measurement of portal haemodynamics by hepatic vein catheterization will be performed pre-dose and at 1 and 2 hours after start of the infusion on Day 3. Pulmonary artery catheterization will be performed pre-dose and at 2 hours after start of the infusion on Day 3.

Body weight will be assessed pre-dose on Days 1-3, and in the morning on Day 4.

## 6.2 Part 2

Each patient will receive a 2-hour intravenous infusion of FE 204205 or placebo on Day 1.

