### 3.1.2 Overall Design and Control Methods

[figure not shown]
This is a trial investigating the safety, tolerability, pharmacokinetics and pharmacodynamics of FE 204205 in cirrhotic patients with portal hypertension. The trial is divided in two parts:

Part 1 is an open-label investigation of safety, tolerability, pharmacokinetics and pharmacodynamics of increasing intravenous doses of FE 204205 and will include 6 patients. Dosing will take place in a staggered fashion, with one patient completing dosing before the next patient will be dosed (i.e. with at least 3 days between administration of the first dose in one patient and the first dose in the next patient). Systemic and portal haemodynamics will be assessed by pulmonary artery and hepatic vein catheterization on Day 3. Each patient will receive three ascending doses of FE 204205, given once daily as 2-hour infusions on three consecutive days. Dose escalation on Days 2 and 3 will only commence provided that the increase in mean arterial

pressure from baseline is  $<15$  mmHg, absolute mean arterial pressure  $\leq 120$  mmHg, systolic blood pressure  $\leq 160$  mmHg, diastolic blood pressure  $\leq 100$  mmHg, and heart rate  $\geq 55$  beats per minute at any of the vital signs assessments during the 4 hours after start of infusion on the previous day. If these criteria are not met, the same dose will be administered the next day. If the increase of dose results in non-tolerable effects, the preceding tolerated dose will be reverted to for the remaining administrations in that patient.

For the first 3 patients, the initial treatment given on Day 1 will be a single dose of 0.01 mg FE 204205 followed by planned doses of 0.025 mg FE 204205 on Day 2 and 0.05 mg FE 204205 on Day 3. For the remaining 3 patients, the planned single doses are 0.025 mg FE 204205 on Day 1, 0.05 mg FE 204205 on Day 2 and 0.1 mg FE 204205 on Day 3. After the first 3 patients have completed all Visit 2 assessments, a Safety Review Committee (SRC) will evaluate the preliminary safety, tolerability, and pharmacodynamics data of the FE 204205 and will decide if the dosing regimen can be increased as planned, or if a modified (lower) dose regimen should be applied (see Figure 3-3).

6 subjects divided in 2 cohorts (3+3):

**Figure 3-3:** Suggested trial design for the 6 patients in Part 1.

\*SRC = Safety Review Committee.

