The chosen dose increments between dose levels (increasing by a factor of 2.5 from the starting dose, then maximum increase of factor 2 for the subsequent doses) are lower and thus more conservative than the ones used in the trials with healthy subjects, where a factor of  $\sim 3$  was applied for the respective dose range from 0.005 mg/hr to 0.05 mg/hr.

In Part 2 each patient will receive a 2-hour intravenous infusion of the dose of FE 204205 selected by the SRC, or placebo, on Day 1. The SRC will select the dose based on incidence and frequency of adverse events, safety laboratory data, ECG, systemic and portal haemodynamic parameters. The dose selected will be the maximum tolerated dose (MTD) or a lower dose. The MTD is defined as the dose level below the dose where one or more stopping criteria, as confirmed by a second measurement, are met in at least two subjects in Part 1.

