#### **7.1.4 Clinical Laboratory Variables**

##### **Clinical chemistry, and haematology**

In Part 1, blood samples for safety laboratory evaluations of clinical chemistry and haematology parameters ([Table 7-1](#)) will be collected at screening, on Day -1, 6 hours after start of intravenous infusion of FE 204205 on Days 1-3, in the morning of Day 4, and at the follow-up visit.

In Part 2, blood samples for safety laboratory evaluations of clinical chemistry and haematology parameters ([Table 7-1](#)) will be collected at screening, on Day -1, 6 hours after start of intravenous infusion on Day 1, in the morning of Day 2, and at the follow-up visit.

The actual sampling times will be recorded. The clinical chemistry, and haematology analyses will be performed locally. Clinically significant abnormal findings will be reported as AEs.

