##### **Urinalysis**

Urine samples for safety laboratory evaluation of urinalysis parameters ([Table 7-1](#)) will in Part 1 be collected at screening, on Day -1, 6 hours after the start of the intravenous infusion of FE 204205 on Days 1 to 3, in the morning of Day 4, and at follow-up.

In Part 2, urinalysis samples will be collected at screening, on Day -1, 6 hours after the start of the intravenous infusion on Day 1, in the morning of Day 2, and at follow-up.

Urinalysis will be performed locally from a sample of mid-stream urine by means of a dip-stick test. In case any result of the dipstick is abnormal, a new urine test will be performed. In case any result of the dipstick is abnormal and clinically significant, a new urine test will be performed. If the abnormal result is confirmed, further examination may be initiated at the discretion of the Investigator. Clinically significant abnormal findings will be reported as AEs.

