### **Date and Time of Onset**

The date of onset is the date when the first sign(s) or symptom(s) were first noted. If the adverse event is an abnormal clinically significant laboratory test or outcome of an examination, the onset date is the date the sample was taken or the examination was performed.

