#### **9.6.2.3      Clinical laboratory variables**

Clinical chemistry and haematology parameters will be summarised in terms of absolute values and changes from baseline to each scheduled post-baseline time point. Shift tables will be presented for changes in category (below, within, or above the normal range) from baseline, presented by treatment. Urinalysis parameters will be summarised by treatment and time point.

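### In Part 1 only the Day 3 dose has a next-morning safety laboratory sample, so a late change after the Day 1 or Day 2 dose is first sampled after the next infusion, and no rule assigns it to a dose

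*Combined protocol and SAP*

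**What the plan says.** Three places give the same Part 1 schedule. Footnote 1 of Table 6-1 reads: "Blood samples for safety laboratory evaluations will be collected 6 hours after start of infusion on Days 1-3, and in the morning on Day 4". Section 7.1.4 repeats it for clinical chemistry and haematology, adding follow-up: "6 hours after start of intravenous infusion of FE 204205 on Days 1-3, in the morning of Day 4, and at the follow-up visit". The urinalysis paragraph of the same section has the same pattern: "6 hours after the start of the intravenous infusion of FE 204205 on Days 1 to 3, in the morning of Day 4". None schedules a safety laboratory sample on the morning of Day 2 or Day 3.

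Other assessments differ. The Table 6-1 footnotes put ECG, vital signs and body weight pre-dose on each of Days 1-3. Blood for pharmacokinetics "will be collected pre-dose and at 0.5, 1, 2, 3 and 4 hours after the start of the infusion on Days 1-3", and blood biomarkers and urine are also collected pre-dose on those days. In Part 2, footnote 1 of Table 6-2 gives the single dose both a 6 h and a next-morning laboratory sample.

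On use of the data, Section 9.6.1 presents Part 1 by dose level and time point, and Section 9.6.2.3 adds: "Shift tables will be presented for changes in category (below, within, or above the normal range) from baseline, presented by treatment". For an adverse event that is a laboratory finding, Section 8.2.2 says "the onset date is the date the sample was taken or the examination was performed". Section 3.5.4 makes these data an input to the Part 2 dose: "The SRC will select the dose based on incidence and frequency of adverse events, safety laboratory data, ECG, systemic and portal haemodynamic parameters".

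**The concern.** Part 1 gives each patient consecutive daily doses, and its data inform the dose carried into Part 2. After the Day 1 and Day 2 doses, laboratory observation before the next infusion ends at 6 h. A change in, say, troponin I or creatinine that develops overnight is first sampled 6 h into the next infusion day. By then it cannot be told apart from an early effect of the newer dose. The Day 3 dose does not have this gap.

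At stake is whether the SRC and the trial report can place a laboratory change with the dose that preceded it, and whether dose levels are tabulated on equal numbers of samples.

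**Working it through.** **Inputs.** The sampling times are those above. Table 5-1 and Section 3.1.2 give the planned doses: patients 1-3 receive "0.01 mg FE 204205 followed by planned doses of 0.025 mg FE 204205 on Day 2 and 0.05 mg FE 204205 on Day 3"; patients 4-6 receive 0.025, 0.05 and 0.1 mg on Days 1, 2 and 3. Section 8.1 gives a terminal half-life of about 3 h and a residual effect of 5 half-lives. The plan states no figure of its own on this point to reproduce.

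**Samples per dosing day, before the next dose or discharge.** Day 1: 1 (6 h). Day 2: 1 (6 h). Day 3: 2 (6 h and the morning of Day 4). The follow-up sample, 4-11 days after the last dose, is left out because it follows all three doses.

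**Samples per planned dose level.**

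| Dose | Administrations | Samples | Per administration | With next-morning sample |
|---|---|---|---|---|
| 0.01 mg | 3 (patients 1-3, Day 1) | 3 × 1 = 3 | 1.0 | 0 of 3 |
| 0.025 mg | 6 (patients 1-3, Day 2; patients 4-6, Day 1) | 6 × 1 = 6 | 1.0 | 0 of 6 |
| 0.05 mg | 6 (patients 1-3, Day 3; patients 4-6, Day 2) | 3 × 2 + 3 × 1 = 9 | 1.5 | 3 of 6 |
| 0.1 mg | 3 (patients 4-6, Day 3) | 3 × 2 = 6 | 2.0 | 3 of 3 |

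A next-morning sample exists for 6 of 18 patient-dose days, so 12 of 18 (67%) lack one.

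**Timing.** The residual-effect window is 5 × 3 h = 15 h. The infusion lasts 2 h, so the 6 h sample falls 6 − 2 = 4 h after it ends: 4/15 = 27% of the window has passed and 73% remains. With first-order decay, 0.5^(4/3) = 0.40 of the end-of-infusion concentration is left. Assuming 24 h between infusion starts, the next safety sample comes 24 + 6 = 30 h after the earlier dose started and 6 h after the later one. Anything arising between 6 h and 24 h is first sampled there.

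**Dating.** Section 8.2.2 gives such a finding the date of that sample, the later dosing day. Section 8.1 counts everything from the first infusion to the last Day 4 assessment as treatment emergent. Neither assigns a finding to a particular Part 1 dose.

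**Illustration of what unequal counts could do.** Assume every sample has the same probability p of being out of range at every dose, and that a patient counts as flagged if any sample is. With one sample the probability is p. With two samples of within-patient correlation r it is 2p − p² − r·p(1 − p), so the two-to-one ratio is 2 − p − r(1 − p).

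- r = 0: 1.95 at p = 0.05, 1.90 at p = 0.10, 1.80 at p = 0.20.
- p = 0.10: 1.90 at r = 0, 1.45 at r = 0.5, 1.18 at r = 0.8, 1.00 at r = 1.
- Share of two-sample flags not seen with one sample, p = 0.10: 47%, 31%, 15% and 0% at those four values of r.

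The documents give neither p nor r, and specify no any-flag analysis.

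**After the fix.** With a pre-dose sample on Days 2 and 3, the counts are 6 in 3, 12 in 6, 12 in 6 and 6 in 3: 2.0 per administration at every level.

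**The case against.** The strongest reply is that the planned presentation already handles most of this. Section 9.6.1 and the summaries in Section 9.6.2.3 are by scheduled time point, so 6 h is compared with 6 h and the Day 4 morning stands apart. This stands: the unequal count does not bias those summaries. It does not settle the shift tables, described as by treatment with no time point stated, and it cannot show whether a Day 2 or Day 3 value at 6 h began before that day's infusion. Section 9 defers analysis detail to a separate SAP. That could add an attribution rule, but it cannot supply missing samples.

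Decision impact is also limited, and this too stands. The within-patient escalation criteria, and the stopping criteria that define the maximum tolerated dose, use no laboratory values. Lactate is sampled at 3 h after every dose. Investigators record causality and actual sampling times. Laboratory data are one of several inputs to an expert review of six patients.

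A reader might infer three stronger things that the documents do not support:

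- That all lower doses have half the laboratory follow-up of the top dose. This is true of 0.01 and 0.025 mg; 0.05 mg averages 1.5/2.0 = 75%.
- That late abnormalities are recorded against a higher dose. The onset rule fixes only a calendar date, and Section 3.1.2 repeats the dose when the escalation criteria are not met.
- That the by-dose laboratory comparison is tilted nearly twofold. That needs an any-flag analysis and independent samples. Samples taken within a day in one patient are likely to be positively correlated, so 1.80 to 1.95 is the upper end. Nor can one abnormality be both lost and carried forward: if it resolves before the next sample it is missed; if it persists it is seen but placed later.

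**Conclusion.** The concern holds as a gap in the schedule, not as a demonstrated bias. The sample counts follow directly from Tables 5-1 and 6-1, assuming escalation proceeds as planned. A change arising after 6 h on Day 1 or Day 2 is first observed and dated after the next infusion, which is a higher dose only if escalation occurs. No analysis of the present schedule can separate it from an early change after that infusion.

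The shift tables, laboratory adverse events and the SRC's use of laboratory data can be affected. The size cannot be derived from the documents; the illustrative ratio runs from 1.95 down to 1.0 according to assumptions they do not supply. The case for change rests on low cost and on consistency with Part 2 and with the other Part 1 assessments.

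**What to change.** In footnote 1 of Table 6-1 and in Section 7.1.4, for both blood and urinalysis, add a pre-dose safety laboratory sample on Days 2 and 3, using the pre-dose blood draws and urine collections already scheduled. Present it as the next-morning time point of the previous day's dose, as the Day 4 morning sample is for the Day 3 dose. In Section 9.6.2.3, state that Part 1 shift tables are by dose level and time point, so that the Day 4 morning is not pooled with 6 h.

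Cost: 2 extra samples × 6 patients = 12 local blood analyses, 12 dipsticks, slightly more blood drawn, and a few lines of text. If no sample is added, the shift-table sentence alone equalises the comparison at no cost, but leaves late and early changes inseparable. No dose, escalation or stopping rule is changed.
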